## PrEP4Her Analysis Plan

**Specific Aim 3: Pilot PrEP4Her, refined through Aim 2, to deliver PrEP for Black cis-gender women attending routine gynecologic care visits.**

Started September 26, 2025

### Objectives

(Primary manuscript) Mixed methods paper evaluates the implementation outcomes, using the RE-AIM framework, of the PrEP4Her intervention in a low barrier gynecology setting.

(Primary/Fidelity) Described fidelity to PrEP4Her from the end-user perspective. Describe results from survey, compare/contrast with EHR review (EHR data confirms the number of PrEP prescriptions)

**Study population:** Reproductive aged women 18-45 who received the PrEP4Her intervention as a component of their standard care from January 2023 – August 2024 [Pre-implementation stage Jan – July 2023; PrEP4Her implementation July 2023 January 2024; Pilot January 2024-August 2024].

**PreP4HER components** - Universal sexual history screener, synchronous PrEP training, job aides [pocket cards with CDC PrEP guidance and 5Ps, EHR documentation/order aids, educational materials, asynchronous training on communication strategies

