**PrEP4Her Study Design:** PrEP4Her, a multi-component implementation strategy with components defined as well as refined through prior aims, will be evaluated through a one-arm pilot at a university-affiliated GYN clinic. (**Figure 3**) We have chosen a one-arm trial because PrEP is not currently being offered routinely at GYN clinics and there are three Black cis-gender women on PrEP in the university-affiliated PrEP clinic, making a comparison either between other GYN clinics or between our PrEP clinic have limited meaning. Implementation processes will result from communication with our CAB and consultant ([name]). Upon completion of PrEP4Her development, we will begin engaging key GYN staff, practice managers and clinicians to begin training as well as implementing job and documentation aids within the clinic. Educational materials will be placed in all areas where patients are seen within the clinic. We will monitor implementation outcomes for PrEP4Her over a 6-month timeframe, with detailed procedures that we have described in the below section.

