**Procedures for Evaluating Proximal Implementation Outcomes:**

**Reach Outcome:** For this study outcome, Reach (i.e. the number of individuals who are willing to participate in an initiative) is defined as the absolute number of Black cis-gender women who receive a PrEP prescription. We will also evaluate the proportion of women prescribed PrEP who had a PrEP indication. PrEP indication will not be defined using the Center for Disease Control and Prevention (CDC) PrEP indication clinical guidelines due to evidence suggesting these criteria are too restrictive and may not predict risk. Instead we will define PrEP eligibility based on the CDC’s guidance summary criteria, deeming those PrEP eligible who meet any of the following criteria for cis-gender women not living with HIV (over a 6-month timeframe): HIV-positive sex partner, bacterial STI (gonorrhea or syphilis), more than one sex partner, inconsistent condom use, sex for exchange of goods, or being in a high-prevalence network. This data will be obtained based on the sexual risk screener (a component of implementation strategy) documented in the chart during patient visits.

**Procedures.** Data will be collected from the university’s electronic medical record, looking at visit data for all cis-gender women with clinic visits during the pilot timeframe. We will be able to extract prescription data directly, but PrEP eligibility and referral will require review of chart documentation.

**Preliminary Effectiveness Outcome:** To evaluate effectiveness of PrEP4Her, we will determine increases in PrEP prescriptions over-time. We will also evaluate what patient factors are associated with PrEP prescription.

**Procedures.** A data extraction of the UAB electronic medical record will be done (as described above) at 3-month time intervals after implementation of PrEP4Her (i.e. baseline, 3-months and 6-months’ time). We will collect the following patient demographics: age, race, ethnicity, and insurance status.

**Statistical analysis.** Frequencies for prescription will be reported overall and for each independent variable (i.e. patient demographics), at each of the 3 time points (baseline, 3 months and 6 months). Means, standard deviations and t-test comparisons between those referred and prescribed PrEP will be reported for continuous

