#### Quantitative data

1. Visits per period (of intervention) with number of PrEP prescriptions
  - a. Patient visits by intervention period; total n=4161
  - b. PrEP prescriptions per period; n=11
2. EHR review (to confirm PrEP prescriptions)
  - a. Total charts reviewed n= 4635; missing =6
3. Demographics of all patients
  - a. Race
  - b. Sex at birth assignment
  - c. Gender in EHR
  - d. Lab results
    - i. Chlamydia
    - ii. Gonorrhea

- iii. Syphilis
- iv. HIV

4. Demographics of patients with a PrEP prescription

- a. Race
- b. Sex assigned at birth
- c. Gender assigned in HER
- d. Lab results
  - i. Chlamydia
  - ii. Gonorrhea
  - iii. Syphilis
  - iv. HIV

5. Sexual health pre-screener survey; n=1135

- a. Sociodemographics
  - i. Race
  - ii. Sex assigned at birth
  - iii. Gender in EHR
  - iv. Lab results
    - 1. Chlamydia
    - 2. Gonorrhea
    - 3. Syphilis
    - 4. HIV
- b. Sexual health pre-screener outcomes; n=1135
  - i. Types of sexual behaviors
  - ii. Gender of partners
  - iii. Sexually active in last year
  - iv. Number of sexual partners in past year
- c. Data on when participants were seen (by month/year)

6. Post visit (fidelity) survey data; n=242

- a. Demographics
  - i. Race
  - ii. Education
  - iii. Employment
  - iv. Insurance
  - v. Estimated household income
  - vi. Reason for visit
  - vii. Anal sex in past 6 months
  - viii. Condom use history
  - ix. Number of partners
  - x. Gonorrhea or syphilis diagnosis, past 6 months
  - xi. Partner living with HIV and not on medication
  - xii. Did provider take sexual history?

- xiii. Saw educational materials during visit?
- xiv. Spoke with provider about PrEP?
- xv. Prescribed PrEP during visit?

- b. Fidelity items
  - i. Comfort discussing PrEP w/ provider
  - ii. Understood side effects of PrEP after discussion w/ provider
  - iii. Provider discussed how to pay for PrEP
  - iv. Felt confident could take PrEP daily after visit
- c. Row percentages -Talked to doctor about PrEP and demographics

7. PrEP prescriptions data with physician and intervention period

- a. Demographics of patient prescribed; n=11
  - i. Race
  - ii. Age
  - iii. Lab results
  - iv. Earliest Emtricitabine-Tenofovir
  - v. Study Prescription Date
  - vi. Order Date

8. Number of women with a PrEP indication seen during the study visit (no indication/STI in last 12 months/multiple partners/STI in last 12 months and multiple partners); n=4241

- a. Data by visit date

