### **Procedures:**

- a. **Visit data for all cis-gender women with clinic visits during the pilot timeframe**
- b. **PrEP prescription data**

- c. **PrEP eligibility and referral data**
- 2. **Preliminary Effectiveness:** Defined by increases in PrEP prescriptions over time. We will also evaluate what patient factors are associated with PrEP prescription.

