**Procedures:**

- a. **Frequencies of PrEP prescriptions by**
- b. **Report demographics of patients prescribes PrEP**
- 3. **Adoption:** Defined as the proportion of key-stakeholders within our pilot site who were willing to initiate our implementation strategy.

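### As written, the SAP's before/after assessment of preliminary effectiveness does not support a quantified change in prescribing: the population wording contradicts itself, two months fall in two stages each, and no rate or interval is specified.

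*Combined protocol and SAP*

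**What the plan says.** **Population and stages.** The SAP (Objectives, Study population) covers "Reproductive aged women 18-45 who received the PrEP4Her intervention as a component of their standard care from January 2023" to August 2024. The bracket that follows gives a pre-implementation stage from January to July 2023, then "PrEP4Her implementation July 2023 January 2024; Pilot January 2024-August 2024". No day-level dates are given.

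**Effectiveness measure.** SAP Paper 1, item 2 (Preliminary Effectiveness) is "Defined by increases in PrEP prescriptions over time". The protocol (Aim 3, Preliminary Effectiveness) extracts records "at 3-month time intervals after implementation of PrEP4Her" and reports prescription frequencies "at each of the 3 time points (baseline, 3 months and 6 months". For the observation window, the protocol (Aim 3, Study Design) says: "We will monitor implementation outcomes for PrEP4Her over a 6-month timeframe".

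**Data available.** SAP Quantitative data, item 1, lists "Patient visits by intervention period; total n=4161" together with prescriptions per period, 11 in total. Item 7 lists the prescriptions with intervention period and several date fields. Neither the 4161 visits nor the 11 prescriptions are split by stage.

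**Baseline.** The protocol reports no PrEP prescriptions at the pilot site at the time of writing (B1; C3, Hypothesis).

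**The concern.** A before/after statement needs a baseline group, a boundary between before and after, and a measure that allows for different amounts of observation. Each is incomplete here.

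- Women seen before implementation cannot have received the strategy, so the population sentence conflicts with its own first stage.
- Two months sit in two stages. The SAP does not say whether the middle stage counts as before, after or neither.
- Neither document turns the count into a rate or attaches an interval, although visits by period are listed.

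The protocol hypothesises an increase from zero. Section C6 makes preliminary efficacy one of three conditions, with feasibility and acceptability, for applying for a full trial. The same section values the work without it, so the harm is confined to the before/after statement. There, a reader given counts alone could not separate more prescribing from more observation, and would see no uncertainty around 11 events.

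**Working it through.** The documents give no sample size, power or effect size for Aim 3, so there is no design figure to reproduce.

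**Inputs.** Stage months (SAP, Study population); 11 prescriptions and 4161 visits (SAP, Quantitative data, item 1). Assumptions: August 2024 is included, visit volume is even over time, and prescriptions are independent.

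**1. Overlap.** Counted inclusively, the stages last 7 + 7 + 8 = 22 months, but January 2023 to August 2024 has 20 calendar months. The excess is July 2023 and January 2024, each counted twice.

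**2. Stage length.** Assigning each shared month to one stage gives:

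| July 2023 to | January 2024 to | Months (pre / implementation / pilot) | Pilot ÷ pre |
|---|---|---|---|
| pre | implementation | 7 / 6 / 7 | 1.00 |
| pre | pilot | 7 / 5 / 8 | 1.14 |
| implementation | implementation | 6 / 7 / 7 | 1.17 |
| implementation | pilot | 6 / 6 / 8 | 1.33 |

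A mid-month split (6.5 / 6 / 7.5) gives 7.5/6.5 = 1.15, inside this range. In the most unequal case, a constant rate gives expected counts of 11 × 6/20 = 3.30 (pre) and 11 × 8/20 = 4.40 (pilot), a difference of 1.1 prescriptions. If an analyst pooled both later stages, the length ratio would be 13/7 = 1.86 or 14/6 = 2.33.

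**3. Overall rate.** 11/4161 = 2.64 per 1,000 visits. The exact Poisson 95% limits for 11 events are 5.49 and 19.68. Divided by 4161, these give 1.32 to 4.73 per 1,000.

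**4. Sensitivity to one prescription.** Take both later stages pooled against pre-implementation. Let U be the Clopper-Pearson upper 95% limit for the share of the 11 prescriptions that fall in the pre stage. The lower limit of the rate ratio (later ÷ pre) is (1 − U)/U × (pre months ÷ later months).

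- 0 of 11 in pre: U = 1 − 0.025^(1/11) = 0.285. The lower limit is 0.715/0.285 × 7/13 = 1.35, or × 6/14 = 1.08.
- 1 of 11 in pre: U = 0.413. The lower limit is 0.587/0.413 × 7/13 = 0.77, or × 6/14 = 0.61.

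Suppose one prescription is dated July 2023 and none earlier. Placing July in implementation gives 0 of 11 with 6/14, a lower limit of 1.08. Placing July in pre-implementation gives 1 of 11 with 7/13, a lower limit of 0.77. The same records then fall on either side of 1.

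**The case against.** Much of the other side's case stands.

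- **Baseline of zero.** A reader might infer that no statement of increase is possible. The documents do not support that. The protocol reports zero prescriptions at the site when it was written, so any later prescriptions are a descriptive increase on that figure. However, no document gives the January to July 2023 count, so the size of a before/after change remains open.
- **Denominator.** Item 1 already pairs visits with prescriptions by period. The gap is only that the effectiveness section does not say the result will be a rate, or give it an interval.
- **Intent.** Listing a pre-implementation stage shows that a baseline is meant, and other SAP items refer to all patients. A reader might infer that baseline women were dropped. Nothing shows this; the fault is in the wording.
- **Length artefact.** It is tempting to say that counts would probably rise with no change in prescribing. With pooled later stages and a constant rate, the chance that the later count exceeds the baseline count is P(Bin(11, 0.65) ≥ 6) = 0.85 or P(Bin(11, 0.70) ≥ 6) = 0.92. But neither document plans that pooling, and the calculation presumes 3.30 to 3.85 baseline prescriptions against a reported zero. For pilot versus baseline the length effect is small and would not explain a rise from zero.
- **Broken line.** The SAP procedure that stops at "Frequencies of PrEP prescriptions by" may have lost text in extraction. Nothing here relies on it.
- **Shorthand dates.** Contiguous month ranges are ordinary shorthand, and the data set already carries a period variable. This makes the repair easy, but the cut-offs still need to be published, because step 4 shows they can matter.

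**Conclusion.** The point holds in limited form. The population sentence contradicts itself, two of 20 months are assigned twice, the middle stage has no stated role, and effectiveness has no rate or interval. A quantified before/after change is therefore not supported as written.

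Unequal length matters little for pilot versus baseline. The greater sensitivity is to the dating of individual prescriptions: one event moved into baseline takes the lower limit from above 1 to below 1. That result assumes even visit volume and a pooled contrast that the documents do not plan, and the true stage split is unknown. Severity is minor to moderate, with medium confidence.

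**What to change.** 1. Define the population as all women aged 18-45 with a clinic visit in each stage, whether or not they received any component.
2. Give non-overlapping stage dates and state how the middle stage is treated.
3. Report prescriptions per 1,000 visits by stage with exact Poisson 95% intervals, using the item 1 visits as denominator, for Black women (the Reach population) and for all women.
4. State that these rules were set after data collection, with the total of 11 prescriptions known. The SAP is dated September 2025 and already contains that total.

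Optional clarifications: a descriptive rate ratio (lower limit only if the baseline count is zero); which item 7 date field assigns the stage; how the protocol's 3- and 6-month points map to the stages; and the units of 4161, 4241 and 4635. Using either of the other totals as denominator would move the overall rate only to 11/4241 = 2.59 or 11/4635 = 2.37 per 1,000.

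The cost is SAP wording and minor reprogramming on data already listed. Intervals will be wide with 11 events, and no narrower for Black women alone. Rules fixed now are post hoc: they make the choice visible but do not remove the analyst's freedom.

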### Outcomes Assessment

#### Qualitative data- Grounded in Sekhon, et al. acceptability framework

1. 7 key informant interviews
2. 18 participant interviews

#### Quantitative data

1. Visits per period (of intervention) with number of PrEP prescriptions
  - a. Patient visits by intervention period; total n=4161
  - b. PrEP prescriptions per period; n=11
2. EHR review (to confirm PrEP prescriptions)
  - a. Total charts reviewed n= 4635; missing =6
3. Demographics of all patients
  - a. Race
  - b. Sex at birth assignment
  - c. Gender in EHR
  - d. Lab results
    - i. Chlamydia
    - ii. Gonorrhea

- iii. Syphilis
- iv. HIV

4. Demographics of patients with a PrEP prescription

- a. Race
- b. Sex assigned at birth
- c. Gender assigned in HER
- d. Lab results
  - i. Chlamydia
  - ii. Gonorrhea
  - iii. Syphilis
  - iv. HIV

5. Sexual health pre-screener survey; n=1135

- a. Sociodemographics
  - i. Race
  - ii. Sex assigned at birth
  - iii. Gender in EHR
  - iv. Lab results
    - 1. Chlamydia
    - 2. Gonorrhea
    - 3. Syphilis
    - 4. HIV
- b. Sexual health pre-screener outcomes; n=1135
  - i. Types of sexual behaviors
  - ii. Gender of partners
  - iii. Sexually active in last year
  - iv. Number of sexual partners in past year
- c. Data on when participants were seen (by month/year)

6. Post visit (fidelity) survey data; n=242

- a. Demographics
  - i. Race
  - ii. Education
  - iii. Employment
  - iv. Insurance
  - v. Estimated household income
  - vi. Reason for visit
  - vii. Anal sex in past 6 months
  - viii. Condom use history
  - ix. Number of partners
  - x. Gonorrhea or syphilis diagnosis, past 6 months
  - xi. Partner living with HIV and not on medication
  - xii. Did provider take sexual history?

- xiii. Saw educational materials during visit?
- xiv. Spoke with provider about PrEP?
- xv. Prescribed PrEP during visit?

- b. Fidelity items
  - i. Comfort discussing PrEP w/ provider
  - ii. Understood side effects of PrEP after discussion w/ provider
  - iii. Provider discussed how to pay for PrEP
  - iv. Felt confident could take PrEP daily after visit
- c. Row percentages -Talked to doctor about PrEP and demographics

7. PrEP prescriptions data with physician and intervention period

- a. Demographics of patient prescribed; n=11
  - i. Race
  - ii. Age
  - iii. Lab results
  - iv. Earliest Emtricitabine-Tenofovir
  - v. Study Prescription Date
  - vi. Order Date

8. Number of women with a PrEP indication seen during the study visit (no indication/STI in last 12 months/multiple partners/STI in last 12 months and multiple partners); n=4241

- a. Data by visit date

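### Does listing the three delivery questions under Demographics leave the SAP's Paper 2 without a usable fidelity outcome?

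*Combined protocol and SAP*

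**What the plan says.** The protocol's Fidelity section under Specific Aim 3 picks out three components of the strategy that patients can report on: sexual history screening, receipt of PrEP educational material, and a conversation with a provider about PrEP. Survey questions 1 to 3 ask about these. Question 4 is open-ended and goes only to women who had the conversation; it asks what was said and how it felt. The closed questions are to be summarised descriptively and the open answers coded qualitatively. The stated purpose is to gauge type III error, that is, whether a weak result could reflect a strategy that was not delivered.

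The SAP lists the data under Quantitative data. Item 6 is headed "Post visit (fidelity) survey data; n=242" and has three parts:

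- 6a, Demographics, has 15 entries. The last four are "Did provider take sexual history" (xii), "Saw educational materials during visit" (xiii), "Spoke with provider about PrEP" (xiv) and "Prescribed PrEP during visit" (xv).
- 6b, Fidelity items, has four entries: "Comfort discussing PrEP w/ provider", "Understood side effects of PrEP after discussion w/ provider", "Provider discussed how to pay for PrEP", and confidence about taking PrEP every day.
- 6c plans row percentages for having talked to the doctor about PrEP, by demographics.

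The SAP's Objectives ask for a description of the survey results and a comparison with the record review. Paper 2 defines fidelity in general terms, as in the protocol, and its one-line procedure refers to the patient survey without naming any question.

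**The concern.** Read literally, the SAP moves the protocol's fidelity measures into a respondent-characteristics table and gives the fidelity label to a different set. The difference matters because the two sets answer different questions. The three delivery questions can be put to every respondent and can record that something did not happen. Understanding of side effects after a discussion presupposes, by its wording, that there was a discussion; comfort in discussing PrEP does so by implication. A woman who had no such conversation has nothing to rate.

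A fidelity conclusion drawn only from 6b could therefore look favourable among women who had the conversation and say little about how many did. That would defeat the protocol's reason for measuring fidelity. Because Paper 2 names no items, nothing in its own text rules this out.

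**Working it through.** There is no stated figure to reproduce. The check is an item-by-item comparison.

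**Step 1. Match the protocol's survey questions to the SAP's lists.**

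| Protocol, Aim 3, Fidelity | SAP, item 6 |
|---|---|
| Question 1, sexual history taken | 6a.xii |
| Question 2, educational material seen | 6a.xiii |
| Question 3, PrEP discussed with a provider | 6a.xiv |
| Question 4, how the conversation went (open; only women who had it) | nearest is 6b.i, comfort |

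Of the three protocol measures, 3 of 3 are in 6a and 0 of 3 are in 6b. Of the four 6b questions, 0 of 4 is one of the three measures. The misplacement is real. Nothing has been dropped.

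**Step 2. Ask how much the 6a heading means.** Race, education, employment, insurance and household income are demographic: 5 of 15 entries. The other 15 − 5 = 10 are not. Setting aside the three delivery questions leaves 10 − 3 = 7: reason for visit, anal sex, condom use, number of partners, gonorrhea or syphilis diagnosis, a partner with untreated HIV, and PrEP prescribed at the visit. The same habit appears elsewhere in the list. Items 3 and 4 put laboratory results under demographics, and item 7a adds prescription and order dates. The SAP uses the word for almost any variable describing a patient, so its use here is weak evidence that outcomes were reassigned.

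**Step 3. Look for planned uses of the 6a entries as outcomes.**

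- 6a.xiv (PrEP discussed) is the variable tabulated in 6c against demographics, so the SAP does not treat it as a demographic. Whichever way the table is laid out, it shows how many women had no conversation.
- 6a.xv (PrEP prescribed) is the survey counterpart of the prescription count that the Objectives have confirmed from the record.
- 6a.xii (history taken) has a second source: Adoption in Paper 1 includes a chart count of patients who were screened.
- 6a.xiii (materials seen) has no separate line, but it is a listed question in the survey that the Objectives say will be described.

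**Step 4. Ask what Paper 2 would have to do for the harm to occur.** It would have to report 6b alone, although all of item 6 carries the fidelity heading, the objective covers the survey as a whole, and its own definition asks whether the strategy was carried out as planned. The 6b questions do not answer that definition by themselves; the 6a questions do.

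**Step 5. Ask whether 6b would conceal non-delivery even then.** The documents do not give the skip rules or response options for 6b. If every respondent was asked, the question on payment could itself register non-delivery. If only women who discussed PrEP were asked, the number answering, set beside 242, would reveal the shortfall, assuming that item-level counts are shown and that few answers are missing for other reasons.

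**The case for a change.** The best case for a change is that the label is the only place where the SAP assigns particular questions to fidelity, and it points away from the protocol. Item 6c covers one of the three measures and does not call it the fidelity outcome. Whether the strategy was delivered is a live question, since the SAP records 11 prescriptions against 4,161 patient visits (11/4,161 = 0.26%). Timing adds to this: the analysis plan was started on September 26, 2025, after the pilot ended in August 2024, and already contains realised counts. Naming the outcome set would protect Paper 2 from the suspicion that it chose after seeing the data, and it would cost almost nothing.

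Some of this stands. The heading is wrong for entries xii to xiv, and Paper 2 is terse. Had the protocol been silent on what fidelity means, naming the items would be needed. But the protocol names the three components, fixed before the pilot, in the same combined document, and the SAP repeats its general definition. An analyst who wants to know which questions measure delivery has somewhere to look and finds one answer. A report that left them out would be departing from the protocol, and the protocol's own text would show it.

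Nor is the 6b set foreign to the protocol. Question 4, on how the conversation went, belongs to the same fidelity survey and is analysed under the same section. Comfort in discussing PrEP carries that theme into a closed question. Reporting 6b beside the delivery questions extends the protocol's assessment.

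**Conclusion.** No change to the plan follows. The three delivery questions are filed under the wrong sub-heading, which is a clerical slip, and Paper 2 leaves a detail unstated that the protocol supplies. All 3 of 3 measures are collected and listed. Correcting the label would alter no question, no planned frequency and no denominator. The fidelity analysis is descriptive, in a one-arm pilot, with no test, decision threshold or sample size attached, so no effect size is at stake.

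This rests on three assumptions: that Paper 2 describes the whole post-visit survey, as the SAP's objective says; that the protocol's list of components governs where the SAP does not name items; and that the number answering is shown for each 6b question, since the documents do not say who was asked. All three are ordinary practice for a descriptive survey report. The authors may tidy the list when they draw up the tables, but the plan is workable as it stands.

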## **Paper 1: Mixed Methods Paper, guided by REAIM**

Procedures for Evaluating Proximal Implementation Outcomes:

**1. Reach:** For this study outcome, Reach (i.e. the number of individuals who are participated in PrEP4Her) is defined as the absolute number of Black cis-gender women who receive a PrEP prescription. We will also evaluate the proportion of women prescribed PrEP who had a PrEP indication.

PrEP eligibility is based on the CDC's guidance summary criteria, deeming those PrEP eligible who meet any of the following criteria for cis-gender women not living with HIV (over a 6-month timeframe): HIV-positive sex partner, bacterial STI (gonorrhea or syphilis), more than one sex partner, inconsistent condom use, sex for exchange of goods, or being in a high-prevalence network. This data will be obtained based on the sexual risk screener.

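### SAP item 8 counts PrEP indication on two criteria with a 12-month STI window, which contradicts the SAP's own six-criterion, 6-month definition

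*Combined protocol and SAP*

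**What the plan says.** The SAP describes PrEP indication in two places.

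- **Outcomes Assessment, Quantitative data, item 8.** The label is "Number of women with a PrEP indication seen during the study visit" and the levels are "no indication/STI in last 12 months/multiple partners/STI in last 12 months and multiple partners); n=4241". Item 8a adds a breakdown by visit date.
- **Paper 1, Reach.** The rule is "deeming those PrEP eligible who meet any of the following criteria for cis-gender women not living with HIV (over a 6-month timeframe"), and the list opens with "HIV-positive sex partner, bacterial STI (gonorrhea or syphilis), more than one sex partner, inconsistent condom use, sex for exchange of goods" and closes with membership of a high-prevalence network. The same section sets the outcome that uses the rule, "We will also evaluate the proportion of women prescribed PrEP who had a PrEP indication", and names a source: "This data will be obtained based on the sexual risk screener".

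The protocol's Reach Outcome (Aim 3) gives the same six criteria and the same 6-month window. It adopts them in place of the clinical-guideline indication, which it considers too restrictive, and it says that eligibility will need chart review. Among the Reach procedures in the SAP, the matching entry is only "PrEP eligibility and referral data", with no dataset attached.

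**The concern.** The protocol and the SAP's Reach section treat indication and eligibility as one construct. Item 8 uses the same term for a variable built on a different rule, and nothing in the SAP calls it a proxy or explains the 12-month window. If it is reported under its present label, readers will take it as the count of women meeting the plan's definition.

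Two results are exposed. One is item 8's own tabulation. The other is the secondary Reach proportion, if an analyst takes indication status from the only dataset that carries that name. The main Reach result, the number of Black women prescribed PrEP, needs no indication status and is not at stake.

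**Working it through.** **1. The two rules side by side**

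| Element | Item 8 | Reach definition |
|---|---|---|
| Criteria represented | 2 | any of 6 |
| STI type | not stated | gonorrhea or syphilis |
| STI look-back | 12 months | 6 months |
| More than one partner | yes, no window | yes, 6 months |
| HIV-positive partner | no level | qualifies |
| Inconsistent condom use | no level | qualifies |
| Exchange sex | no level | qualifies |
| High-prevalence network | no level | qualifies |

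Criteria not represented: 6 − 2 = 4. Ratio of STI look-backs: 12/6 = 2.

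**2. Women classed differently**

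- A woman whose only criterion is one of the last four rows is eligible under Reach but falls into the no-indication level of item 8.
- A woman whose only criterion is gonorrhea 7 to 12 months ago is counted as indicated in item 8 but is not eligible under Reach.
- Chlamydia is among the lab results the SAP lists. If item 8's STI includes it, a woman with chlamydia alone is a further case of the second kind.

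**3. Direction.** Dropping four criteria can only lower the count with an indication. A longer STI window and an unrestricted STI type can only raise it. Item 8's partner window is unstated; a past-year window, as in the pre-screener (item 5b), would also raise it. The documents give no frequencies, so the net sign is unknown.

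**4. Sensitivity of the Reach proportion.** Items 1b and 7a give 11 prescriptions and 11 patients prescribed. With a base of 11, each woman reclassified moves the proportion by 1/11 = 9.1 percentage points. The number who would be reclassified is not given.

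**5. Women who cannot be classified.** Item 8 has no unknown level. The pre-screener has n=1135, and 1135/4241 = 26.8%. Suppose the screener were the only source on partners and each screener record matched at most one item 8 record. Then at least 4241 − 1135 = 3106 records (3106/4241 = 73.2%) would have no partner data, and item 8 could place them only in the no-indication or STI-only level. Chart review may fill some of this gap; the SAP does not say.

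**6. The count of 4241.** No derivation is given, so there is no calculation to reproduce. No sum or difference of the SAP's other counts (4161, 4635, 6, 1135, 242, 11), each used at most once, comes within 2 of 4241. Against item 1a, "Patient visits by intervention period; total n=4161", the excess is 4241 − 4161 = 80 (80/4161 = 1.9%). Against the 4635 charts reviewed, the shortfall is 394 (394/4635 = 8.5%), or 4629 − 4241 = 388 (8.4%) after the 6 missing.

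**The case against.** The strongest reply is that the Reach section already settles its own rule. The proportion, the six criteria and the data source stand together under one outcome, and no outcome in the SAP refers to item 8. On that reading item 8 is an available data table with a loose label. This stands. A reader might infer that the Reach proportion will be computed on the two-criterion variable, but the documents do not say so. What remains is a risk of misuse, because the Reach procedures name no dataset.

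A reader might also infer that the six-criterion rule cannot be applied to the data collected. That goes too far. The listed pre-screener outcomes do not name condom use, HIV-positive partner, exchange sex or network, but chart review is foreseen in the protocol. The post-visit survey (item 6, n=242) lists condom use, number of partners, gonorrhea or syphilis in the past 6 months, a partner with HIV who is not on medication, and whether PrEP was prescribed. Four of the six criteria are thus at least partly represented there, although linkage to the prescribed women is not described.

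Finally, 4241 looks impossible as a count of women beside 4161 visits. It would be, if both covered the same period and item 8 counted unique women. The SAP states neither, the n includes women with no indication, and item 8a is by visit date. Nor is 4241 the denominator of any stated outcome. It is an unexplained count, not a demonstrated error.

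**Conclusion.** The contradiction in definition is explicit and needs no assumption beyond reading indication and eligibility as one construct, as both documents do. As written, item 8 represents two of the six criteria, uses twice the STI look-back, and misclassifies women in both directions under the plan's own rule.

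The consequence for Reach is conditional. It arises only if item 8 is used for the secondary proportion, and it is then 9.1 points per woman reclassified, taking the 11 prescriptions as 11 women. The documents support neither a claim of bias in a given direction nor any effect on the main Reach count. The 73.2% without partner data is likewise conditional on the screener being the only source. Severity is minor to should-fix: the label is wrong for the plan's definition, and correcting it is cheap.

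**What to change.** 1. State that the Reach proportion among the 11 prescribed women uses the six-criterion, 6-month definition, and give the source of each criterion: screener, chart review, labs, or the post-visit survey if it can be linked.
2. Either recode item 8 to that definition, or relabel it as a two-criterion proxy with a 12-month STI window, state its STI type and partner window, and do not report it as indication or eligibility under the Reach definition.
3. In item 8, do not default women without partner or STI data to the no-indication level. Show them as unknown.
4. As a secondary clarification, state whether 4241 counts women, visits or charts, and over what period.

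The cost is SAP wording plus a relabel or recode of existing data. Some chart review is needed only if all six criteria are used.
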